### **8.3 Enrollment**

Subjects will be enrolled from 2 to 5 days prior to the Day 1 visit. Enrollment should be done after the subject has completed the screening assessments and after it has been determined that the subject meets all the inclusion and exclusion criteria.

Assess eligibility status for inclusion into the trial based on protocol inclusion/exclusion criteria, including results from screening lab assessments.

### **8.4 Day 1 Visit**

Subjects should fast for at least 8 hours (overnight) prior to this visit. The Day 1 visit assessments will serve as the baseline assessments.

1. The medical history should be reviewed and updated to include any changes occurring since the screening visit.
2. Assessment of eligibility
3. Vital signs (temperature/pulse/supine blood pressure)
4. Physical examination (including weight)
5. Hematology ([Appendix A](#))
6. Serum chemistry ([Appendix A](#))
7. Urinalysis
8. Serum hormones ([Appendix A](#))
9. Bone turnover markers ([Appendix A](#))
10. Record the usage of any concomitant medications and ongoing treatments.
11. Adverse events (ongoing on Day 1)
12. Caprini VTE Risk Assessment ([Appendix D](#))
13. Blood samples for pharmacokinetic assessment
14. Assess hot flashes

15. Dispense study drug
16. First dose- Instruct the subject to take his capsule at the same time each day

### **8.5 Day 14 Visit**

The following assessments will be conducted on Day 14 ( $\pm$  3 days):

1. Vital Signs
2. Serum Chemistry – ([Appendix A](#))
3. Record the usage of any concomitant medications and treatments
4. Adverse events

### **8.6 Day 30 and Day 60 Visit**

Subjects should fast for at least 8 hours (overnight) prior to these visits. The following assessments will be conducted on Day 30 ( $\pm$  7 days) and Day 60 ( $\pm$  7 days):

1. Vital Signs (temperature/pulse/supine blood pressure)
  2. Serum chemistry – (Appendix A)
  3. Hematology – (Appendix A)
  4. Serum hormones– (Appendix A)
  5. Blood samples for pharmacokinetic assessment
  6. Record the usage of any concomitant medications and treatments.
  7. Assess hot flashes (see [Appendix C](#))
  8. Caprini Venothromboembolism Risk Assessment ([Appendix D](#))
- It is important to note that it is expected that the patient population included in this study will have some risk of VTE due to age, presence of a malignancy, and BMI. The purpose of this assessment is a change in risk from baseline. Also, while the questionnaire is designed for the patient to complete, in this study, the Caprini VTE risk assessment should be filled out by study personnel with information from the patient and patient's chart.

If there is an increase in risk from baseline (Day 1) in this assessment, appropriate preventative actions should be taken. The subject should be consulted about the risk for VTE and actions that would increase their risk further such as long periods of inactivity and surgery. Prophylactic anticoagulation therapy should be considered.

Prolonged PTT-LA, dRVVT and Protein C and/or Protein S deficiency are not exclusionary from the study. However, if a patient has a prolonged PTT-LA, a prolonged dRVVT or is deficient for Protein C and/or Protein S, and remains eligible for participation in the study, prophylactic anticoagulation therapy should be considered.

For Protein C or Protein S deficiency, consideration should be given to dietary changes to increase Vitamin K intake.

9. Adverse events
10. Collect capsule bottles and perform capsule accountability/compliance assessment
11. Dispense study drug

### **8.7 Day 84 Visit (End of Study Visit)**

Subjects should fast for at least 8 hours (overnight) prior to this visit. The following assessments will be conducted on Day 84 ( $\pm 7$  days):

1. Vital Signs (temperature/pulse/supine blood pressure)
2. Physical examination (including weight)
3. Serum chemistry ([Appendix A](#)) (central laboratory)
4. Hematology ([Appendix A](#)) (central laboratory)
5. Serum hormones ([Appendix A](#)) (central laboratory)
6. Blood samples for pharmacokinetic assessment
7. Bone turnover markers
8. Record the usage of any concomitant medications and treatments
9. Adverse events
10. Assess hot flashes (see [Appendix C](#))
11. Caprini Venothromboembolism Risk Assessment ([Appendix D](#))
  - It is important to note that it is expected that the patient population included in this study will have some risk of VTE due to age, presence of a malignancy, and BMI. The purpose of this assessment is a change in risk from baseline. Also, while the questionnaire is designed for the patient to complete, in this study, the Caprini VTE risk assessment should be filled out by study personnel with information from the patient and patient's chart.

If there is an increase in risk from baseline (Day 1) in this assessment, appropriate preventative actions should be taken. The subject should be consulted about the risk for VTE and actions that would increase their risk further such as long periods of inactivity and surgery. Prophylactic anticoagulation therapy should be considered.
12. Collect capsule bottles and perform capsule accountability/compliance assessment

## **8.8 Follow-up Visit**

The following assessments will be performed 30 days ( $\pm$  7 days) after the End of Study visit (Day 84):

1. Vital Signs (temperature/pulse/supine blood pressure)
2. Physical examination (including height and weight)
3. Adverse events

## **8.9 Pharmacokinetic Sampling**

### **8.9.1 Blood Samples**

Samples of venous blood for the determination of trough plasma concentrations of VERU-944 and related metabolites will be obtained on Days 1 (prior to dose), 30, 60 and 84. The sample should be taken prior to dosing with VERU-944 on these days. The time of the last dose of study drug prior to the clinic visit (day before visit) and the time of the blood samples should be carefully recorded.

The blood samples should be collected in a 6 mL K2EDTA blood collection tube at each collection time.

Immediately after collection, the tubes will be gently inverted several times to mix the anticoagulant with the blood sample. Blood samples may be kept on wet ice (the use of ice packs in a water bath is also acceptable) for up to 20 minutes until processed. The plasma fraction will be separated by placing the collection tube into a centrifuge for 10 minutes at 1,500 x g. The plasma fraction will be withdrawn by pipette and divided into two polypropylene freezing tubes (with each tube receiving approximately equal aliquots). All plasma samples will be placed into a freezer at -20°C (or below) within 1 hour after collection. (NOTE: A flash freezing in dry ice or liquid nitrogen is NOT required under this protocol but may be used.)

Any remaining plasma samples after completion of the protocol outlined pharmacokinetic analysis may be used to identify and quantify the metabolites of VERU-944 or measure other biomarkers of safety or efficacy.

### **8.9.2 Plasma Sample Labels**

The plasma freezing tube labels will contain the following information:

- Subject Number
- Study Number
- Site Number
- Nominal Day Collection
- Aliquot Number: Aliquot A or B
- Species and Matrix: Human Plasma
- Sample Sequence Number

- Barcode Number

Labels will be fixed to freezing tubes in a manner that will prevent the label from becoming detached after freezing.

All plasma samples will be stored frozen (-20°C or below). Details of the method validation and sample analysis will be included with the final report.

### **8.10 Rules for Subjects that Become at High Risk for the Development of Venous Thromboembolic Events during the Study**

If a subject has any of the events listed below during the study, they are considered to have an increased risk of development of a VTE. The subject should be monitored closely and prophylactic anticoagulation therapy should be used if clinically indicated. These subjects are not required to discontinue the study if these events occur:

1. Surgery
2. Hospitalization
3. Trauma, such as a broken long bone
4. Radiation therapy to prostate for cancer control (radiation to bone to relieve pain is acceptable)
5. Prolonged immobilization

If a subject is expecting to have a prolonged immobilization such as a long car ride or plane ride or sitting at a desk for a long period of time, the subject should be instructed carefully about proper steps to take to prevent VTEs. Specifically, subjects should be instructed to, whenever possible, get up and walk around (at least every two hours) and flex your feet up and down while sitting by alternating raising your toes off the floor while keeping your heels on the floor and then pointing your toes. Subjects should also wear compression stockings if long periods of inactivity are expected.

The Caprini Venothromboembolism Risk Assessment (Appendix E) rules and instructions should be followed. However, it is important to note that it is expected that the patient population included in this study will have some risk of VTE due to age, presence of a malignancy, and BMI. The purpose of this assessment is to monitor for increased risk from baseline. The events listed above will increase the risk of VTEs in these patients.

### **8.11 Subject Stopping Rules**

If, in the opinion of the investigator, the participation in the study is or is becoming detrimental to the well-being of a particular subject, this issue should be discussed with the Medical Monitor for this study and dosing may be discontinued.

Subjects that experience a Grade 3 or greater toxicity according to the Common Terminology Criteria for Adverse Events (CTCAE) version 4

([https://evs.nci.nih.gov/ftp1/CTCAE/CTCAE\\_4.03\\_2010-06-14\\_QuickReference\\_5x7.pdf](https://evs.nci.nih.gov/ftp1/CTCAE/CTCAE_4.03_2010-06-14_QuickReference_5x7.pdf)) that is deemed to be possible, probably or definitely related to study drug will be discontinued from the study. Prior to discontinuation from the study, the grading of the event and causal relationship should be discussed with the Medical Monitor for the study.

Subjects will be discontinued from dosing if AST or ALT levels are >5 times the upper limit of normal, or if AST or ALT levels are >3 times the upper limit of normal along with a total bilirubin elevation of >2 times the upper limit of normal.

### **8.12 Early Discontinuation of Study Treatment**

A subject will be considered to have completed the trial if they received at least 84 days of treatment with VERU-944 or the study is terminated by the sponsor. Subjects may prematurely discontinue study treatment for any of the following reasons:

1. Consent Withdrawn (specify the reason).
2. Significant and unacceptable adverse event – specify the adverse event leading to discontinuation
3. Investigator decision (specify the reason), must be approved by the Medical Monitor
4. Non-compliance by subject with protocol requirements, must be approved by the Medical Monitor
5. Lost to follow-up (record the date of last contact)
6. Death (specify the following information)
  - a. Date of death
  - b. Death due to primary disease? Yes or no
  - c. Death due to study drug? Yes or no
  - d. Death due to adverse event? Yes or no
7. Study terminated by the Sponsor
8. Other reason (specify the reason) should be approved by the Medical Monitor

The reason for discontinuation of study treatment will be documented for each subject. Subjects who discontinue prematurely will not be replaced. If a subject is discontinued from the study, he will be asked to complete all End of Study visit assessments and return all study materials (study medication and electronic device). At the time of discontinuation, please fill out the End of Study case report forms (eCRFs) and subject disposition eCRF pages.

### **8.13 Adverse Events**

An adverse event (AE) is any unfavorable or unintended change in body structure (signs) or body function (symptoms), abnormal laboratory result that is associated with symptoms or requires treatment, or worsening of a pre-existing condition. This includes all such events regardless of the presumed relationship between the event and the study medication(s).

Any AE that occurs after the informed consent is signed but prior to dosing on Day 1 will be captured as part of the medical history and will be documented on the appropriate eCRF. This would include AEs resulting from concurrent illnesses, reactions to concomitant medications or progressive disease states. These AEs will be captured as part of the medical history.

Each subject will be assessed for the development of any adverse events. Adverse events should be assessed at each visit to the clinic. This information should be obtained in the form of non-leading questions (e.g., "How are you feeling?") and from signs and symptoms detected during each examination, observations of the study personnel or spontaneous reports from the subjects.

Any AEs such as complaints, signs, or symptoms that occur during the course of the study or designated follow-up periods will be recorded on the subject's case report form (eCRF). This would include AEs resulting from concurrent illnesses, reactions to concomitant medications, or progressive disease states.

Whenever possible, the AE will be described on the case report form using standard medical terminology consistent with Common Terminology Criteria for Adverse Events (CTCAE) version 4 in order to avoid the use of vague, ambiguous or colloquial expressions. The investigator will evaluate all adverse events as to their intensity, relation to test medication, outcome and action taken.

Each AE will be evaluated for duration, intensity, and relationship to (or association with) the study treatment (or other causes). Additionally, the actions taken (e.g., reduction of dosage, discontinuation of study medication, administration of treatment, etc.) and the resulting outcome of the AE will be indicated on the case report form.

Any subject who is withdrawn from the study due to an adverse event will be followed until the outcome of the event is determined, and the investigator will prepare a written summary of the event and document the available follow-up information on the case report form.

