As mentioned above, the rationale for the loading dose is to achieve steady state quickly to meet the Food and Drug Administration (FDA) requirement for the demonstration of efficacy at Day 28 of dosing (FDA Draft Guidance for Industry, 2003: Estrogen and Estrogen/Progestin Drug Products to Treat Vasomotor Symptoms and Vulvar and Vaginal Atrophy Symptoms – Recommendations for Clinical Evaluation). Based upon the published 14.2–33.4 day half-life of cis clomiphene (Szutu et al., 1989), without a loading dose, evaluation of efficacy as reflected by the steady state will not be achieved until after Day 28. Therefore, Veru has developed a dosing regimen for this study that includes loading doses (see [Table](#) below).

Cis-clomiphene, as part of the FDA approved product Clomid, has been used in men for off-label acute and chronic indications with limited reported safety observations. However, in an ongoing nonclinical toxicology study of VERU-944 in rats and beagle dogs, preliminary indications are that the dose of VERU-944 required to treat hot flashes in men with prostate cancer on ADT is between 10-50 mg (data on file). Moreover, at a high dose of cis-clomiphene of 20 mg/kg/day (a human equivalent dose of 667 mg in a 60 kg human) in male dogs, dose limiting toxicities have been observed. The dose limiting toxicities that have been observed include elevations in liver function tests (AST, ALT, alkaline phosphatase, GGT, and total bilirubin), weight loss and death. No significant toxicities have been observed in the ongoing study in rats. Due to the preliminary information that suggests a dose of VERU-944 up to 50 mg per day will show efficacy and safety in the proposed indication, Protocol V72203 has been amended so that the 100 mg dose of VERU-944 will not be used until and unless the dose of 50 mg VERU-944 has been shown to not be effective for the proposed indication and an acceptable side effect profile is determined at the blinded placebo, 10 mg and 50 mg doses of VERU-944 in Stage 1.

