### **8.13.1 Intensity of Adverse Events**

The intensity of the AEs will be graded according to CTCAE version 4. For any adverse event that is not specifically covered in CTCAE version 4, the following criteria should be used:

---

Grade	Description
1	Mild; asymptomatic or mild symptoms; clinical or diagnostic observations only; intervention not indicated
2	Moderate; minimal, local or noninvasive intervention indicated; limiting age-appropriate instrumental activities of daily living
3	Severe or medically significant but not immediately life-threatening; hospitalization or prolongation of hospitalization indicated; disabling; limiting self-care activities of daily living
4	Life-threatening consequences; urgent intervention indicated.
5	Death related to AE

If the intensity (Grade) changes within a day, the maximum intensity (Grade) should be recorded. If the intensity (Grade) changes over a longer period of time, the changes should be recorded as separate events (having separate onset and stop dates for each grade).

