#### 6.4.5 Laboratory Parameters

Laboratory data (Section 9.2) will be displayed by treatment group and overall for the safety population. Continuous data for laboratory tests of serum chemistry, hematology, urinalysis, and serum hormone including change from baseline will be descriptively summarized at each visit, and urinalysis categorical data will be summarized by visit. The number of subjects who have values outside the normal range will also be displayed descriptively at each time point.

A listing of serum chemistry, hematology, urinalysis, and serum hormone test results will be presented separately by visit. The numeric values will be flagged/indicated with LN = Low Normal, LP = Low Panic, N = Normal, HN = High Normal, HP = High Panic in the listing.

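### A symptom-free man taken off drug under the liver stopping rule need not be recorded as an adverse event, and no planned output counts men by arm at the protocol's own liver thresholds

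*Protocol*

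**What the plan says.** - **Definition (Protocol 8.13).** Besides signs, symptoms and worsening of existing conditions, the definition covers an "abnormal laboratory result that is associated with symptoms or requires treatment".
- **Actions taken (Protocol 8.13).** The examples are "reduction of dosage, discontinuation of study medication, administration of treatment, etc".
- **Liver rule (Protocol 8.11).** "Subjects will be discontinued from dosing if AST or ALT levels are >5 times the upper limit of normal". A second limb combines AST or ALT above 3 times the upper limit of normal (ULN) with total bilirubin above 2 times ULN. Neither limb mentions symptoms, causality or recording as an adverse event.
- **Separate toxicity rule (Protocol 8.11).** A Grade 3 or greater toxicity "that is deemed to be possible, probably or definitely related to study drug will be discontinued from the study".
- **Follow-up (Protocol 8.13).** "Any subject who is withdrawn from the study due to an adverse event will be followed until the outcome of the event is determined".
- **Laboratory output (SAP 6.4.5).** Continuous values and changes from baseline are summarised by visit and arm. Values are listed with flags that separate high-normal from high-panic. In addition, "The number of subjects who have values outside the normal range will also be displayed descriptively at each time point".
- **Background (Protocol 7.2.3).** In male dogs, "The dose limiting toxicities that have been observed include elevations in liver function tests", together with weight loss and death.

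**The concern.** The event definition and the stopping rule use different tests. One asks whether the man has symptoms or needs treatment; the other asks only how high the laboratory value is. A raised transaminase without symptoms can meet the second and fail the first.

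If sites apply the definition as written, some of the stops that the protocol itself requires will not appear among the adverse events. The summary by preferred term, the listing of events leading to discontinuation and the duty to follow to outcome all begin from the recorded event, so one omission carries through all three. If sites differ in how they read the definition, the same case is recorded at one and not at another.

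**Working it through.** No formula in the plan bears on this, so the check traces one hypothetical man through the documents: no symptoms, no treatment given, ALT above 5 times ULN at a scheduled visit.

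1. **Is dosing stopped?** Yes, under 8.11, on the value alone.
2. **Is he an adverse event under 8.13?** He has no symptoms. Stopping the drug does not obviously count as requiring treatment, because 8.13 lists discontinuing study medication and giving treatment as separate actions. On the stated wording, no.
3. **Which discontinuation reason applies (8.12)?** Reason 2 requires an adverse event. No reason is given for a laboratory stop. Reasons 3 (investigator decision) and 8 (other) are available; each must be specified, and both refer to Medical Monitor approval.
4. **Where does he appear?**

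| Output | Does he appear? |
|---|---|
| TEAE tables and listing of adverse events leading to discontinuation (SAP 6.4.1) | Not necessarily |
| Disposition by arm and reason (SAP 6.2.1) | Yes, but possibly under a reason that does not say liver |
| Laboratory summaries by visit and arm (SAP 6.1.1, 6.4.5) | Yes; the maximum would reflect an extreme value |
| Out-of-range counts (SAP 6.4.5) | Yes, pooled with every smaller elevation |
| Flagged laboratory listings (SAP 6.4.5) | Yes, individually |
| Count of men by arm at the 8.11 thresholds | No such output is planned |

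5. **Can the existing laboratory tables stand in for a threshold count?** Not fully. A maximum shows one value, not how many men exceeded a limit. Separate summaries of ALT and bilirubin cannot show whether both were raised in the same man, which is what the second limb of 8.11 asks. Entry permits ALT or AST up to 2 times ULN (exclusion 8), so a man can be out of range before his first dose. The listings hold the information, but someone would have to count by hand.
6. **Is he followed?** If he leaves the study, 8.12 and 8.16 call for the final-visit evaluations, which include serum chemistry (8.7). The Follow-up visit (8.8) has vital signs, physical examination and adverse events, but no chemistry. The duty to follow to outcome attaches to men withdrawn from the study because of an adverse event. He fails the adverse-event condition, and since the liver rule speaks of stopping dosing rather than leaving the study, he may fail the other condition too.

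**Scale.** The documents give no expected rate of liver stops, so these are assumed counts of unrecorded cases per arm. Planned arms are about 30, with a maximum of 40 (Protocol 9.1).

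| Unrecorded men | Arm of 30 | Arm of 40 |
|---|---|---|
| 1 | 1/30 = 3.3% | 1/40 = 2.5% |
| 2 | 2/30 = 6.7% | 2/40 = 5.0% |
| 3 | 3/30 = 10.0% | 3/40 = 7.5% |

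**The case against.** The best case for the plan is that other provisions already deal with this man. The reason for stopping must be documented and is counted by arm. Laboratory values are summarised with maxima and listed with panic flags. Chemistry is repeated at withdrawal. The Safety Review Team reviews safety data, not only adverse events, at least monthly (Protocol 9.3.4.1). An investigator could also report him as a serious adverse event, whose definition in 8.13.3 is broad, as an event of clinical interest (8.13.4), or under the Grade 3 rule.

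Most of that stands, and it limits the point. It does not close the gap, because the reporting routes depend on medical judgement or on a causality assessment, and none says that a stop under the liver rule is an adverse event.

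Four stronger readings are tempting, and the documents do not support them.

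- **That such a man would be uncounted and the signal lost.** SAP 6.2.1 and 6.4.5 count and list him. What is missing is his place among the adverse events and a count at the thresholds.
- **That 8.13.1 contradicts 8.13.** Its Grade 1 text, "Mild; asymptomatic or mild symptoms; clinical or diagnostic observations only; intervention not indicated", is a fallback scale for grading events that CTCAE does not cover. It grades something already accepted as an adverse event and does not define one.
- **That the Stage 2 decision would be misled by missing by-arm event counts.** Stage 1 safety is reviewed blinded for that decision (Protocol 2.0 and 7.2.3, SAP 6.7), and nothing confines the blinded report to adverse event tables.
- **That liver toxicity is the trial's established dose-limiting risk.** It is one of several findings in dogs, at a stated human equivalent of 667 mg, or 667/50 = 13.3 times the 50 mg maintenance dose. No significant toxicities were reported in the rat study.

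**Conclusion.** The point holds in a limited form. As written, the protocol can require a man to stop drug for liver values and yet not require that stop to be recorded as an adverse event. He can then be absent from the TEAE tables and the listing of discontinuations due to adverse events, and outside the sentence on follow-up to outcome. The laboratory and disposition outputs show him but do not count him as a liver stop by arm.

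This rests on two readings: that the laboratory limb of 8.13 governs laboratory findings, and that stopping drug is not itself treatment, which the list of actions in 8.13 supports. It also assumes that the investigator does not use a discretionary reporting route. The effect is one man, or 2.5% to 3.3% of an arm, per unrecorded case; how many such cases would arise cannot be derived from the documents. Because the data are collected and remain visible elsewhere, this is a cheap improvement rather than an essential correction.

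**What to change.** 1. **Protocol 8.13, reconciled with 8.11 and 8.12.** State that a laboratory abnormality that meets an 8.11 threshold, or leads to study drug being stopped, is recorded as an adverse event with or without symptoms. Reason 2 in 8.12 then applies.
2. **Protocol 8.11 and 8.13.** Reconcile stopping dosing in the one with withdrawal from the study in the other, so that it is clear the existing sentence on follow-up to outcome covers these men.
3. **SAP 6.4.5.** Add the number and percentage of men by arm with any post-baseline AST or ALT above 3 times ULN, AST or ALT above 5 times ULN, total bilirubin above 2 times ULN, and the 8.11 combination in the same man.

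The stopping thresholds are unchanged; the table uses the protocol's own cut-offs and central-laboratory data already collected. The cost is one added sentence, a wording alignment, one table and a few more adverse event records. The reported adverse event rate may look slightly less favourable.
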